4.5 Benefit/risk and ethical assessment

4.5.1 Potential benefits

The potentially improved disease control from adding TRT to the systemic treatment is the most important potential benefit for the participants. For patients with such an aggressive disease as SCLC, prolonged disease control is of outmost importance, as this improves quality of life, maintains functional level, and prolongs survival time. For the health care system, better disease control will reduce the need for resources required to provide optimal care and support.

Hitherto, all SCLC patients are treated equally, though we know from experience that there is a large heterogeneity with respect to treatment response, response duration, symptom development and survival time. ^{19,59} Our knowledge of prognostic and predictive biomarkers in SCLC is in general very limited. The planned translational research may lead to a novel classification system based on molecular markers, with potentially large impacts for both patients and the health care systems.

A classification system will enable us to avoid ineffective, unnecessary, potentially toxic therapy, and patients will avoid spending time for futile therapy. Scientifically, the impact of an improved classification is huge, as it allows for more targeted enrolment in trials that will improve the relevance, feasibility and quality of future research. Targeted enrolment allows for reduced sample sizes, shorter readout time, reduced costs, and increased number of trials that can be conducted.

4.5.2 Overall risks of durvalumab

Monoclonal antibodies directed against immune checkpoint proteins aim to boost endogenous immune responses directed against tumor cells. By stimulating the immune system however, there is the potential for adverse effects (AEs) on other tissues.

Most adverse drug reactions seen with ICIs are due to the effects of inflammatory cells on specific tissues. These immune mediated effects can occur in nearly any organ system and are most commonly seen as gastrointestinal AEs such as colitis and diarrhea, pneumonitis/interstitial lung disease (ILD), hepatic AEs such as hepatitis and liver enzyme elevations, skin events such as rash and dermatitis and endocrinopathies including hypo- and hyper-thyroidism.

Risks with durvalumab include, but are not limited to, diarrhea/colitis pneumonitis/ILD, endocrinopathies (hypo- and hyper-thyroidism, type I diabetes mellitus, hypophysitis and adrenal insufficiency) hepatitis/increases in transaminases, nephritis/increases in creatinine, pancreatitis/increases in amylase and lipase, rash/pruritus/dermatitis, myocarditis, myositis/polymyositis, thyroiditis, pemphigoid, myasthenia gravis, immune thrombocytopenia, and other rare or less frequent inflammatory events including neurotoxicities, infusion-related reactions, hypersensitivity reactions, and infections/serious infections.

In monotherapy clinical studies, most common AEs (all grades) (≥ 15% of patients) are fatigue, nausea, decreased appetite, dyspnea, cough, constipation, diarrhea, vomiting, back pain, pyrexia, asthenia, anemia, arthralgia, peripheral edema, headache, rash, and pruritus. Approximately 9.4% of patients experienced an AE that resulted in permanent discontinuation of durvalumab and approximately 6.5% of patients experienced a serious adverse event (SAE) that was considered to be related to durvalumab. For information on all identified and potential risks with durvalumab, please refer to the current version of the durvalumab IB.

Most of the treatment-related AEs were manageable with dose delays, symptomatic treatment, and in the case of events suspected to have an immune basis, the use of established treatment guidelines for immune-mediated side-effect.

Overall, adding durvalumab to platinum/etoposide chemotherapy in the CASPIAN trial did not

increase the frequency or severity of AEs. The proportion who experiences grade 3-4 toxicity was 62% both among patients who received chemoimmunotherapy and in the control arm. Immune-related AEs occurred in 20% of patients in the durvalumab-arm. Of these, 12/265 (5%) experienced grade 3 or 4 AEs, and one patient died from immune related hepatotoxicity.³⁷

In a small phase I/II study, 10 patients on durvalumab received palliative RT. There were no severe RT-related AEs. ⁶⁰ A phase II trial (n=40) of concurrent chemoradiotherapy to 60-66 Gy and the PD-L1 inhibitor atezolizumab in unresectable NSCLC, did not reveal any indications of increased RT toxicity compared with historical data. ⁵⁶ In the PACIFIC trial, consolidation durvalumab therapy was well tolerated in patients who did not progress after chemoradiotherapy in locally advanced NSCLC. ²⁷ Overall, there are currently no clinical data suggesting that combining chemoimmunotherapy with low-dose TRT causes severe radiotoxicity.

4.5.3 Overall benefit-risk

Results from the CASPIAN trial shows that durvalumab plus platinum/etoposide chemotherapy is well tolerated and prolongs survival. TRT is well tolerated in ES SCLC patients, and studies suggest that concurrent chemo-immunotherapy and TRT is well tolerated in NSCLC. On this basis, we believe that the overall risk is low, and that the experimental therapy may provide a clinically relevant survival benefit for an important group of patients in desperate need for better therapies.

5. Provide summary of overall benefit-risk for the study objectives 5.1 Primary objective(s)

We consider survival the most relevant endpoint for ES SCLC patients. Since we will irradiate lesions in the experimental arm, there are potential methodological issues with using PFS as the primary outcome, since the RECIST criteria consider irradiated lesions non-measurable. Survival may be influenced by post-study therapy, but there is little variation in relapse therapy for ES SCLC. All post-study therapy will be registered.

There is currently no data suggesting whether the combination therapy may provide a synergistic effect or an additive effect. Thus, it is difficult to predict how the PFS-curves may be influenced by adding TRT, and it is consequently difficult to select the most appropriate PFS-endpoint.

In conclusion, we consider 1-year overall survival to be the most appropriate endpoint, it is easily measured, and provides a strong and clinically relevant measure of the potential effect of the experimental therapy. There is no risk associated with this measure.

5.1.1 Secondary objective(s)

In general, the major benefit of ICIs in cancer treatment is that some patients achieve long term survival. Thus, we plan a follow-up of 5 year after last patient entry to accurately assess whether some patients achieve a long term survival. Follow-up time in completed trials of chemo-immunotherapy in ES SCLC was designed with a too short follow-up time to assess survival beyond 2 years.

Current data shows that high-dose TRT can safely be administered concurrently with chemotherapy and checkpoint inhibitors, but we cannot rule out that TRT adds significant toxicity in patients with ES-SCLC. Thus, we will compare frequency and severity of adverse events, as well as patient-reported health-related quality of life, between treatment arms.

PFS may be difficult to accurately assess (see above), but is still of interest, especially when it comes to local control. We assume that adding TRT improves local control, but if there is a synergistic effect of combining RT and durvalumab, the course of disease may also be altered. Thus, assessing the location and timing of metastases is of great interest. Furthermore, a synergistic effect should improve response rates, and to further investigate whether such an effect occurs, we will compare response rates in non-irradiated lesions (i.e. all non-irradiated lesions in the experimental arm compared with overall response rate in the control arm). The role of PCI in ES SCLC is debated. If adding TRT improves efficacy of chemoimmunotherapy, the value of PCI may be small. On the other hand, one can also imagine that TRT plus chemoimmunotherapy improves systemic disease control, and that brain metastases represent a major site for treatment failure.

TRIPLEX
1.1
05-IAN-2022

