1. PROTOCOL SYNOPSIS

Study title: Randomized phase III trial investigating the survival benefit of adding thoracic radiotherapy (TRT) to durvalumab immunotherapy plus chemotherapy in extensive stage small-cell lung cancer

Protocol version number: 1.0

Clinical phase: Randomized phase III

Study duration: From 2021 until 2028

Investigational therapies and reference therapy:

- Reference therapy: Durvalumab plus carboplatin/etoposide
- Investigational therapy: Durvalumab plus carboplatin/etoposide and TRT

Research hypotheses:

The main hypothesis is that adding TRT to durvalumab plus chemotherapy provides a survival benefit for patients with extensive stage (ES) small-cell lung cancer (SCLC).

Specifically, we hypothesize that:

- combining TRT, durvalumab and chemotherapy is feasible and well tolerated
- adding TRT improves survival, response rates, and PFS
- the patients who benefit the most from the study treatment can be identified through analyses of tissue, blood and stool samples
- toxicity of prophylactic cranial irradiation (PCI) is acceptable in ES SCLC patients who receive durvalumab plus chemotherapy

Objectives:

Primary Objective:

To investigate whether adding TRT to durvalumab plus chemotherapy improves 1-year survival.

Secondary Objectives:

To investigate whether adding TRT improves 2-, 3-, 4- and 5-year overall survival.

To investigate whether adding TRT improves overall response rates, response rates in non-irradiated lesions and PFS.

To investigate whether TRT improves local control.

To compare the frequency and severity of adverse events between the treatment arms.

To compare health related quality of life between treatment arms.

Exploratory Objectives:

To compare the duration of severe adverse events between the treatment arms.

To compare the frequency and timing of brain metastases between treatment arms.

To assess cognitive function in the whole study cohort and compare cognitive function between those who receive PCI and those who do not.

To investigate associations between outcomes of study treatment and biomarkers in tissue, blood and stool (e.g. ctDNA in blood, miRNA, gut microbiome).

Endpoints:

Primary Endpoint:

1-year overall survival

Secondary Endpoints:

2-year, 3-year, 4-year and 5-year overall survival

Overall response rates

Response rates in non-irradiated lesions

Progression free survival

Progression free survival in non-irradiated lesions

Local control rates in the thorax

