- Four courses of durvalumab 1500 mg IV day 1, carboplatin (AUC=5, Calvert's formula) IV day 1 and etoposide 100 mg/m² BSA IV day 1. On days 2-4, etoposide is administered in a dose of 100 mg/m² BSA IV or 200 mg/m² BSA PO. Chemoimmunotherapy courses are administered every three weeks. After completing four courses, durvalumab 1500 mg IV is given every four weeks until intolerable toxicity, patient's wish, or disease progression and need for other treatment.
- The dose of durvalumab will be adjusted to 20 mg/kg if a patient's body weight falls below 30 kg
- Patients randomized to the experimental arm will receive TRT of 30 Gy in 10 fractions, one fraction per day, 5 fractions per week, between the second and third chemo-immunotherapy course.
- Patients who achieve a response when evaluated after completion of chemo-immunotherapy may be offered PCI of 25 Gy in 10 fractions or 30 Gy in 15 fractions, one fraction per day, 5 fractions per week according to local treatment policy.

Safety assessments:

Toxicity will be classified according to CTCAE v5.0. Cognitive function will be assessed using the MoCA test. Patients will report HRQoL on the EORTC QLQ C30+LC13.

Efficacy assessments:

OS will be measured from the day of randomization until death by any cause, PFS from the day of randomization until RECIST 1.1 progression or death by any cause. Response to treatment and progression will be assessed according to RECIST 1.1. Response to treatment and progression will be assessed on CT and MRI scans at regular intervals. Sensitivity analyses including measurement of previously irradiated lesions (both thoracic lesions and brain metastases) will be performed.

Statistical methods and data analysis:

Cox proportional hazard method will be used to compare survival. The primary survival analyses will be performed 14 months after the last patient entry (to ensure that 1-year survival data are captured). Pearson's Chi-Square test will be used to compare toxicity, overall response rates, and treatment completion rates. Mann-Whitney's test will be used to compare number of completed chemo-immunotherapy- and durvalumab-courses.

Median OS will be estimated using the Kaplan-Meier method, and a Cox-model will be used for multivariable survival analysis adjusting for established prognostic factors in the target population (sex, PS, disease stage, presence brain metastases and liver metastases) and age. A separate analysis plan will be defined for the biomarker analyses.

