7.1 Inclusion criteria

For inclusion in the study patients must fulfill all the following criteria:

Capable of giving signed informed consent which includes compliance with the requirements and
restrictions listed in the informed consent form (ICF) and in this protocol. Written informed consent
and any locally required authorization (eg, Health Insurance Portability and Accountability Act in the
US, European Union [EU] Data Privacy Directive in the EU) obtained from the patient/legal
representative prior to performing any protocol-related procedures, including screening evaluations.

- 2. Age \geq 18 years at time of study entry.
- 3. ECOG performance status of 0 or 1.
- 4. Body weight >30 kg.
- 5. Adequate normal organ and marrow function as defined below:
 - Haemoglobin ≥10.0 g/dL.
 - Absolute neutrophil count (ANC) ≥1.5 × 10⁹ /L.
 - Platelet count ≥100 × 10⁹/L.
 - Serum bilirubin ≤1.5 x institutional upper limit of normal (ULN). This does not apply to patients with confirmed Gilbert's syndrome (persistent or recurrent hyperbilirubinemia that is predominantly unconjugated in the absence of hemolysis or hepatic pathology).
 - ALT (SGPT) ≤2.5 x ULN unless liver metastases are present, in which case it must be ≤5 x ULN.
 - Measured creatinine clearance (CL) >40 mL/min or Calculated creatinine CL>40 mL/min by the Cockcroft-Gault formula (Cockcroft and Gault 1976) or by 24-hour urine collection for determination of creatinine clearance:

Males Creatinin-clearance (mL/min) = $\frac{\text{Weight (kg) x (140 - age)}}{72 \text{ constraints (kg)}}$

72 x serum creatinine (mg/dL)

remales Creatinin-clearance (mL/min) = $\frac{\text{Weight (kg)} \times (140 - \text{age})}{\text{Version}} \times 0.85$

72 x serum creatinine (mg/dL)

- 6. Patient is willing and able to comply with the protocol for the duration of the study including undergoing treatment and scheduled visits and examinations including follow-up.
- 7. Life expectancy of at least 3 months.
- 8. At least 1 lesion in the thorax, not previously irradiated, that qualifies as a RECIST 1.1 target lesion (TL) at baseline and is possible to irradiate to 30 Gy in 10 fractions. Tumor assessment by computed tomography (CT) scan or magnetic resonance imaging (MRI) must be performed within 28 days prior to randomization.
- 9. Histologically or cytologically confirmed SCLC. Mixed histology may be acceptable as long as the SCLC component accounts for more than 90%.

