8.3.5 Targets for TRT in the present trial

Preferably, the target volume should include the primary lung tumor and regional lymph node metastases identified before chemoimmunotherapy commenced, also in case of a complete response. Extensive, elective nodal irradiation is not allowed.

If possible, all thoracic lesions should be included in the radiotherapy field. If this is not possible, lesions compressing central airways or mediastinal structures (e.g. large vessels and nerves) should be prioritized. A minimum of one lesion should be irradiated. If a complete response is achieved by the time of the CT planning scan, this lesion may be a previously enlarged lymph node.

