8.3.6 Delineation of target volumes

The gross tumor volume (GTV) will include the residual volume after the first (or second) chemoimmunotherapy course. The clinical target volume (CTV) will account for microscopic spread and is generated by expanding the GTV with 5 mm in all directions, but not across anatomic barriers such as trachea, heart, esophagus, bones, except when there is radiological invasion into these structures. The planning target volume (PTV) is defined by expanding the CTV with a margin defined according to local routines.

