14.3.2 Efficacy analyses

For the primary endpoint, the Cox proportional hazards method will be used to compare survival between the treatment groups. Considering that median overall survival was 12-13 months in the two trials that established chemo-immunotherapy as treatment of ES SCLC, the study is designed to perform the primary survival analyses 14 months after last patient entry (to ensure that all survival data at 1 year are captured), which is a timepoint when we believe that the first signal of an effect of the experimental treatment can be seen. Additional survival analyses will be performed 2-, 3-, 4- and 5-year after last patient entry.

Median OS, PFS and time to progression in the brain will be estimated using the Kaplan-Meier method, and a Cox-model will be used for multivariable analyses adjusting for established prognostic factors in the target population (sex, PS, disease stage, presence of brain metastases and liver metastases) and age. Pearson's Chi-square test will be used to compare response rates (overall and in non-irradiated lesions), frequency of brain metastases, and location of metastases.

All HRQoL scores will be transformed to a scale of 0-100 according to the EORTC QLQ scoring manual. Mean scores will be compared at each assessment timepoint. A difference of 10 points is considered clinically relevant. Primary HRQoL-endpoints are dyspnea, global quality of life and physical function. All other HRQoL-scales will be included in complementary analyses.

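### Response in non-irradiated lesions is compared across unlike lesion sets: irradiated thoracic lesions drop out of the experimental rate, while thoracic target disease stays in the control rate

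*Protocol*

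**What the plan says.** The synopsis lists, among the secondary objectives, whether adding TRT improves "response rates in non-irradiated lesions and PFS". Section 14.1 repeats the endpoint without saying which lesions count in which arm. The only definition is in section 5.1.1, where the stated purpose is to look for synergy between radiotherapy and durvalumab: "all non-irradiated lesions in the experimental arm compared with overall response rate in the control arm". Section 14.3.2 names the between-arm test, Pearson's chi-square, which is "used to compare response rates (overall and in non-irradiated lesions").

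Three other provisions decide what those words select:

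- Section 7.1, criterion 8, requires of every patient "At least 1 lesion in the thorax, not previously irradiated, that qualifies as a RECIST 1.1 target lesion (TL) at baseline".
- Section 8.3.5 sets the field in the experimental arm: "If possible, all thoracic lesions should be included in the radiotherapy field", and "A minimum of one lesion should be irradiated".
- Section 7.1, criterion 10, admits stage III patients whose disease is too extensive for limited-stage treatment.

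The synopsis also announces "Sensitivity analyses including measurement of previously irradiated lesions", and section 12.1 describes these for the assessment of progression.

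**The concern.** Randomisation makes the patients comparable. The definition then removes a subset of lesions, chosen by anatomical site, from one arm only. The experimental rate rests on whatever was not irradiated: extrathoracic disease plus any thoracic lesion that could not be put in the field. The control rate rests on everything, including the thoracic target lesion that each control patient has by eligibility.

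If thoracic and other disease respond differently to chemo-immunotherapy, the two rates will differ even when TRT does nothing outside its field. That difference would be read as synergy, or would offset real synergy, and synergy is what this endpoint is meant to examine. The patients scored can differ as well. An experimental patient with all disease in the field has nothing left to evaluate, whereas every control patient can be evaluated.

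**Working it through.** **Which lesions count, by arm**

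| Lesion type | Control rate | Experimental rate |
|---|---|---|
| Thoracic, inside the TRT field (or the equivalent lesion in a control patient) | counted | left out |
| Thoracic, outside the field | counted | counted |
| Extrathoracic | counted | counted, unless itself irradiated |
| Patient with all disease in the field | evaluable | no lesion to score |

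The first and last rows differ between arms. Neither section 14.1, section 14.3.2 nor the synopsis supplies a matching control set. The sensitivity analyses do not help: they measure irradiated lesions again, but do not restrict the control arm to comparable lesions.

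**How much it could matter.** The protocol states no rate, power or sample size for this endpoint, so there is no figure to reproduce. The following is conditional illustration.

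Inputs:

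- Control response 65%. Section 4.1.2 gives this as a background figure for extensive-stage disease; it is not a design rate for the durvalumab control arm.
- Patients per arm: 302 / 2 = 151 (section 14.4, 1:1 randomisation).
- Two-sided 5%, the trial-level alpha, applied nominally to this test.
- Gap *d* between response in the reduced lesion set and in all lesions: assumed. The protocol gives none.

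Method: with x responders out of n in each arm and p̄ = (x_E + x_C)/(n_E + n_C),

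X² = (x_E/n_E − x_C/n_C)² / [p̄(1 − p̄)(1/n_E + 1/n_C)], rejecting at X² ≥ 3.84.

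The rejection probability is the sum of the two binomial probabilities over all outcomes that reject, with p_C = 0.65 and p_E = 0.65 + d.

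No TRT effect outside the field, 151 per arm:

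| Assumed gap d (points) | Rejection, set responds lower | Rejection, set responds higher |
|---|---|---|
| 0 | 4.9% | 4.9% |
| 1 | 5.3% | 5.3% |
| 2 | 6.4% | 6.5% |
| 3 | 8.4% | 8.5% |
| 5 | 14.7% | 15.3% |
| 10 | 43.5% | 47.8% |

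Hand check for d = +5 by normal approximation: p̄ = 0.675. The null standard error is √(0.675 × 0.325 × 2/151) = 0.0539, and the alternative one is √((0.65 × 0.35 + 0.70 × 0.30)/151) = 0.0538. The upper tail is Φ((0.05 − 1.96 × 0.0539)/0.0538) = Φ(−1.03) ≈ 0.151 and the lower tail about 0.002. The total is about 15.3%, as in the table.

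If only 121 experimental patients are evaluable (an assumed 20% loss) against 151 controls, a 5-point gap gives 14% and a 10-point gap 39–43%.

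Masking, with an assumed true out-of-field gain of 15 points (65% vs 80%) and 151 per arm: power is 84% with no gap, 48% if the reduced set responds 5 points lower, and 15% if 10 points lower.

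**The case against.** The best defence is that one rule is being applied to both arms. Control patients receive no routine TRT (section 8.3.11 allows it only on progression), so their non-irradiated lesions are, by and large, all their lesions. This explains the wording. It does not remove the problem, because the same label selects different anatomy in each arm. Nor is the label strictly true of the control arm, since sections 8.4.1 and 8.4.2 allow radiotherapy to brain metastases and other lesions in both arms.

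Second, the definition sits in a rationale paragraph, and section 14 leaves the lesion set open, so an analysis plan could set it without contradicting section 14. That lowers the weight of the point, but section 5.1.1 is the only definition the protocol gives.

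Third, the larger percentages depend wholly on the assumed gap. This objection stands in full: with a gap of 1–2 points the test is close to nominal.

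A reader might go further and infer that the endpoint favours TRT, or that its false-positive rate is 15% or even 48%. The documents support neither. No section gives response by site, so the direction is unknown and the size may be negligible. Nor should one infer that the two sets have nothing in common: thoracic lesions outside the field stay in both.

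**Conclusion.** The point holds as a defect of definition. Section 5.1.1 fixes an asymmetric comparison that confounds lesion site with the out-of-field effect, and nothing elsewhere in the protocol gives the control arm a matching set. Confidence is high for that mismatch and does not extend to its consequence. The rejection and power figures rest on assumed gaps, an assumed 15-point gain and a background rate of 65%; they show sensitivity and do not estimate bias.

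The reach is modest. This is one of several secondary endpoints, and overall response rate remains a separate one. Progression-free survival in non-irradiated lesions (section 14.1) also has no stated control-arm lesion set. The parenthesis in section 5.1.1 covers response only, so the same error cannot be asserted there, but the definition is needed. Primary overall survival, the interim rule and the sample size do not depend on any of this. It should be corrected before response is analysed.

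**What to change.** Replace the parenthesis in section 5.1.1 with: *response in extrathoracic lesions assessable on baseline imaging, in both arms; patients with none are not evaluable for this endpoint in either arm; extrathoracic lesions irradiated outside the TRT field (sections 8.4.1 and 8.4.2) are handled by one rule applied identically in both arms.* The last clause is needed because an extrathoracic set is matched by site but is not free of irradiated lesions. Use the same lesion set for progression-free survival in non-irradiated lesions, and keep overall response rate as its own endpoint.

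This is a change of wording with two costs. Thoracic lesions outside the field are no longer used, and the denominator shrinks. If an assumed 10–20% of patients have no extrathoracic lesion, 151 per arm becomes 151 × 0.90 ≈ 136 to 151 × 0.80 ≈ 121, and power for 65% vs 80% falls from 84% to 80–75%. The rejection rate under no effect stays at about 5%.

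Marking the intended field in every patient before randomisation would keep more lesions, but it is a new procedure at about 25 centres and cannot be done prospectively for patients already randomised. The marks may also not match the final field, which is drawn on the "residual volume after the first (or second) chemoimmunotherapy course".
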